2.8.4.3 Tumor volume and longest dimension

For tumor volume evaluated by MRI (or CT) scanning, descriptive summary of actual tumor volumes as well as its change from baseline will be provided at visits where evaluation is scheduled (Week 26, 48, 72, and 96). For MRI (or CT) images that are not interpretable for tumor volume, the longest dimension (in mm) will be summarized instead. Due to evaluation schedule, this analysis will only be performed for the overall study period.

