7.1.4 Discontinuation of Study drug

Patients may voluntarily discontinue from the study drug for any reason at any time. If a patient decides to discontinue from the study drug, the investigator should make a reasonable effort (e.g. telephone, e-mail, letter) to understand the primary reason for this decision while respecting the subjects rights and record this information in the patient’s chart and on the appropriate eCRF pages. Patients may be considered withdrawn if they state an intention to withdraw, fail to return for visits, or become lost to follow-up for any other reason.

In order to help retain patients in the placebo-controlled phase (Period 1, Weeks 1 - 12), rescue therapy for co-morbid conditions should be optimized before a decision is made to discontinue patients from study drug or from the study.

Patients who discontinue study drug should NOT be considered withdrawn from the study. For patients who discontinue treatment during Weeks 1 - 12, investigators should make reasonable efforts to follow patients and perform all assessments identified for all visits up to and including Week 12 as indicated in [Table 7-1a](#) (Post-treatment follow-up) and [Section 7.1.6](#), even if study drug has been discontinued and alternative cortisol-lowering therapy has been initiated. Patients discontinuing study drug at any time before Week 48 of the Core phase or during the optional Extension phase, should be scheduled for an End of Treatment (EOT) visit as soon as possible, at which time the assessments listed for the EOT visit will be performed ([Table 7-1a](#), [Table 7-1b](#) and [Table 7-2](#)), with the following exceptions:

- Patients discontinuing treatment prior to the Week 36 visit do not need to have an EOT DXA scan
- Patients discontinuing prior to the Week 14 visit or between the Week 26 and Week 36 visits do not need to have an EOT pituitary MRI (or CT) (i.e. scans are needed if patients discontinue within the 12 week period prior to the Week 26 and Week 48 visits).

The date and reason for stopping the study drug should be recorded in the eCRF. If a patient fails to return for the assessments for unknown reasons, reasonable efforts (e.g. telephone, email, letter) should be made to contact them as specified in [Section 7.1.7](#).

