The investigator must discontinue study drug for a given patient if he/she believes that continuation would be detrimental to the patient's well-being. The investigator must also contact the IRT to register the patient's discontinuation from study drug.

Patients must discontinue study drug if any of the following occur:

- Emergence of the following adverse events:
- hypertension defined as office mean supine systolic BP > 180 mmHg or mean supine diastolic BP > 110 mmHg (confirmed and persistent*).
- Any of the following laboratory abnormalities (confirmed):
 - hyperkalemia (serum potassium > 6.0 mmol/L).
 - hypokalemia (serum potassium < 2.8 mmol/L).
- Any of the following laboratory abnormalities (confirmed and persistent*):
 - hyperkalemia (serum potassium > 5.5 mmol/L).
 - hypokalemia (serum potassium < 3.0 mmol/L).
 - hyponatremia (serum sodium < 130 mmol/L).
 - hyperglycemia (fasting plasma glucose \geq 15.0 mmol/L).

* Persistent is defined as unresolved with osilodrostat dose change or after adjustments to other concomitant medications targeting the co-morbidity in question.

- Abnormal liver function as described in [Table 6-2](#).
- Mean QTcF > 500 msec, if the QTc value is confirmed by a cardiologist (see [Section 7.2.2.7](#)).

- Mean QTcF > 480 msec, if the investigator determines it is no longer safe for the patient to continue in the study, based on ECGs, cardiac examination, and recommendation from a cardiologist (see [Section 7.2.2.7](#)).
- Mean increase in QTcF > 30 msec from the mean baseline value at 1.5h post-first dose or the QTcF is > 480 msec at Day 1.
- QTcF increase > 60 msec from the pre-dose measurement earlier during the same visit.
- Pituitary tumor growth, if symptomatic or complicated by compression of the optic chiasm or other structures in and near the sella turcica (visual field loss, cranial nerve palsies, diplopia) and confirmed by MRI of the pituitary (see [Section 7.2.2.5](#)).
- Pregnancy.
- Use of prohibited treatment (refer to [Section 6.4.3](#)).
- Any other protocol deviation that results in a significant risk to the patient's safety.

The appropriate personnel from the site and Novartis will assess whether study drug should be discontinued for any patient whose treatment code has been broken inadvertently for any reason.

The investigator must also contact the IRT to register the patient's discontinuation from study drug within 2 days.

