7.2.2.5 Radiological examinations

Table 7-5 Imaging Assessment collection plan

Procedure	Screening	During Treatment/Extension
Pituitary MRI (or CT)	Mandated at screening	Mandated, approximately every 6 months

Pituitary MRI scanning with gadolinium enhancement will be performed at visits according to [Table 7-1a](#), [Table 7-1b](#), [Table 7-2](#), and [Table 7-5](#). These will be assessed centrally by the imaging vendor to screen for pituitary enlargement either by tumor volume or maximum

dimension of tumor. If MRI scan with intravenous contrast (gadolinium) is contraindicated for a patient, then a non-contrast MRI scan should be performed. If the MRI cannot be performed at all, then a CT of the pituitary (with i.v. contrast if not contraindicated) may be performed. Regardless of imaging type, all regularly scheduled pituitary imaging will be centrally reviewed for consistency in the measurement of dimensions. The modality should remain consistent to that used at baseline unless there is a development of a contraindication. Please see the study imaging manual for further information. If EOT occurs less than 6 months before the scheduled Week 96 visit, MRI (or CT) and DXA is not mandatory at EOT.

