2.8.4 Other safety data

2.8.4.1 ECG and cardiac imaging data

ECG data will be summarized with

- shift table baseline to worst on-treatment result for overall assessments
- Number and percentage of patients with clinically notable QT/QTcF interval values will be summarized.
- listing of ECG evaluations for all patients with at least one abnormality.

The notable criteria for PR are

- > 200 ms post-baseline and \leq 200 ms at baseline
- Increase > 25% compared to baseline to a post-baseline value > 200 ms

The notable criteria for QRS are

- > 110 ms post-baseline and \leq 110 ms at baseline
- Increase > 25% compared to baseline to a post-baseline value > 110 ms

The notable criteria for QT and QTcF are

- > 450 ms at any post-baseline and \leq 450 ms at baseline
- > 480 ms at any post-baseline and \leq 480 ms at baseline
- > 500 ms at any post-baseline and \leq 500 ms at baseline
- an increase from baseline > 30 ms at any post-baseline
- an increase from baseline > 60 ms at any post-baseline

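### Tumor volume is summarised only at four scheduled weeks, with no largest or last value and no rule for end-of-treatment or unscheduled scans, so later-week means can understate growth

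*SAP*

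**What the plan says.** - **Core SAP 2.8.4.3** plans descriptive statistics of tumor volume, with "change from baseline will be provided at visits where evaluation is scheduled (Week 26, 48, 72, and 96". Longest dimension replaces volume where volume cannot be read. The analysis covers the overall study period only.
- **Final SAP 2.8.4.3** keeps the same four weeks, uses central assessment by an independent neuroradiologist, and adds an assessment of whether the tumor extends beyond the sella.
- **Protocol 7.1.4** lists among the mandatory reasons to stop drug: "Pituitary tumor growth, if symptomatic or complicated by compression of the optic chiasm or other structures in and near the sella turcica", with MRI confirmation.
- **Protocol 7.1.4, EOT scans in the core phase:** "scans are needed if patients discontinue within the 12 week period prior to the Week 26 and Week 48 visits". Patients who stop before Week 14 or "between the Week 26 and Week 36 visits do not need to have an EOT pituitary MRI (or CT".
- **Protocol 7.2.2.5** sets routine pituitary imaging as "Mandated, approximately every 6 months". For the extension it says: "If EOT occurs less than 6 months before the scheduled Week 96 visit, MRI (or CT) and DXA is not mandatory at EOT".
- **Tables 2-1 and 2-2 in both SAPs** give core EOT the same visit number as Day 337 (Visit 199) and extension EOT the same number as Day 673 (Visit 299). The core SAP's document history records that the visit window requirement was removed, and the final SAP states no window either.
- **Other safety data** have patient-level extremes. For ECG the core SAP plans a "shift table baseline to worst on-treatment result for overall assessments". Laboratory tests and vital signs have worst-value shift tables in both SAPs, and the final SAP adds the last value for laboratory tests.

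**The concern.** Protocol 2.6 names corticotroph tumor progression as a potential risk, and protocol 8.1.3 makes tumor enlargement a group of adverse events of special interest. The by-week table is the only summary of measured tumor size that the SAPs describe. For this variable, the missing scans at later weeks are caused in part by the outcome itself: a patient stopped for growth contributes to no later scheduled row. A mean among those still being scanned then describes a group from which some of the patients with the most troublesome growth have been removed. The scan that confirmed the growth, if unscheduled, belongs to no row.

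There is a second problem of definition. An EOT scan could be left out, or it could be counted under Week 48 or Week 96 because the visit number is shared. The SAPs do not say which, and the two choices give different tables.

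**Working it through.** The plan states no expected growth, stopping rate or precision for tumor volume, so it has no figure to reproduce. The check sets the rules side by side and then shows the arithmetic of an omitted scan.

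**1. Who leaves because of growth.** Only patients with MRI-confirmed growth that is symptomatic or compressive (protocol 7.1.4). Asymptomatic, non-compressive growth does not force a stop.

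**2. What is scanned after a stop.** Protocol 7.1.4 and 7.1.6 provide an EOT visit and a 30-day evaluation. Scheduled follow-up continues only for stops before Week 12, and only to Week 12. Table 7-1a schedules pituitary imaging at screening only. So a stopped patient has no later scheduled scan.

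**3. When an EOT scan is required in the core phase.** Weeks 14 to 26 and 36 to 48: (26 − 14) + (48 − 36) = 24 of 48 weeks. It is not required in the other 24.

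**4. Where a core EOT scan would land.** In Visit 199, together with Week 48. If pooled there, a required EOT scan could come from as early as Week 14, that is 48 − 14 = 34 weeks before the label on the row.

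**5. Where an extension EOT scan would land.** With the SAP month of 30.4375 days, six months is 6 × 30.4375 = 182.6 days, or 182.6 / 7 = 26.1 weeks. The exemption therefore starts at about Week 96 − 26.1 = Week 69.9. Under Amendment 02, protocol 6.1.5 moves eligible patients between Weeks 48 and 72 out at their next study visit. Exits at Weeks 52, 56, 60, 64 or 68 fall before Week 69.9, so the exemption does not cover them. Those scans belong to neither Week 72 nor Week 96. Under Visit 299 they would sit 96 − 52 = 44 to 96 − 68 = 28 weeks early in a row labelled Week 96. The amendment rationale gives 35 patients in the extension and 10 in the core phase on 10 December 2019. How many exited this early is not stated.

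**6. Illustration of size.** Let N patients have a volume, k of them stop for growth of g%, and the rest have mean change m%. Adding the k stop scans moves the mean from m to [m(N − k) + kg]/N, a shift of k(g − m)/N. Assumptions: N = 69 (the planned enrolment), m = 0, and none of the k scans already in the row.

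| k | g = 25% | g = 50% | g = 100% |
|---|---|---|---|
| 1 | 0.36 | 0.72 | 1.45 |
| 2 | 0.72 | 1.45 | 2.90 |
| 4 | 1.45 | 2.90 | 5.80 |
| 7 | 2.54 | 5.07 | 10.14 |

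Entries are percentage points, for example 4 × 50 / 69 = 2.90. Neither k nor g comes from the documents.

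**The case against.** A reader might infer that any patient whose tumor grows must stop, and that the scans showing growth are all lost from the table. The documents do not support that. Silent growth keeps a patient on drug and in later rows. Growth seen on a routine Week 26, 48, 72 or 96 scan is in the table, and core SAP 2.1 includes the maximum among its descriptive statistics, so a large increase there would show. EOT scans are not excluded; their handling is undefined.

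A reader might also make much of the stops for which no EOT scan is required, such as those between Weeks 26 and 36. That adds little here, because a stop for growth already requires a confirming MRI. What is missing is a place for that scan in the analysis.

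Growth is also reported elsewhere. On-treatment events of special interest are tabulated in both SAPs. The final SAP adds grade, seriousness, action taken and outcome, lists every such event, and assesses spread beyond the sella at each MRI. Reasons for discontinuation are tabulated by period. Exclusion criteria 9 and 10 remove patients at highest risk of chiasm compression, so forced stops may be few. All of this stands, and it means growth would not go unreported. None of it gives the size of the growth.

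Two cautions about the remedy also stand. Protocol 7.2.2.5 promises central review for regularly scheduled imaging, so some unscheduled scans may have only a local reading. A largest-change summary is pushed upward by measurement noise.

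The contrast with ECG is weaker in the final SAP, which drops the shift table, but it still counts notable QT values at any post-baseline time.

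**Conclusion.** The point holds as a gap in a descriptive safety summary. Both SAPs lack a largest or last post-baseline change and a rule for EOT and unscheduled scans. Because some growth forces a stop, means at later weeks can understate growth. The Week 48 and Week 96 rows are also ambiguous, more so with the early exits under Amendment 02.

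The size cannot be derived from the documents. The range of 0.4 to 10.1 percentage points rests entirely on assumed numbers of stops, assumed growth and zero mean change in everyone else; it shows direction and scale only. The primary and key secondary analyses are unaffected, and the point takes no view on the stopping rule itself.

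**What to change.** In section 2.8.4.3 of both SAPs:

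1. Add a per-patient summary of change from baseline to the **largest** and to the **last** post-baseline tumor volume. Use all centrally read MRI or CT scans, including EOT and unscheduled ones, and flag any scan with only a local reading.
2. Where volume is not readable, use longest dimension, tabulated separately in mm. Protocol 10.5.3.4 and core SAP 2.8.4.3 already provide for it; the final SAP text would need it added.
3. State how EOT scans are mapped. Keep early EOT scans out of the Week 48 and Week 96 rows, or show them in a separate EOT row, as final SAP 2.7.7 does for bone density in the extension.
4. Show at each visit the number of patients with a measurement and the cumulative number stopped for tumor growth.

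The cost is one extra table and a mapping rule, with no new procedure for patients. Scans without a central reading would remain flagged. The largest-change column is biased slightly upward by noise and should be read beside the last-value column.

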In addition, treatment with osilodrostat can potentially result in neutropenia, which is considered to be an indirect effect of cortisol reduction, as reported in the literature. During hormonal control, a significant decrease of neutrophil count, which is commonly elevated in patients with Cushing's disease, has been reported demonstrating the effect of glucocorticoids on these blood cells (Masri-Iraqi et al, 2014). This effect has also been observed with osilodrostat in the Cushing's disease trials and has included cases of neutropenia which were associated with mUFC levels that were either below normal or have had a rapid and substantial decline from baseline. In the cases observed, neutropenia has rapidly reversed with discontinuation of osilodrostat, and has also reversed when osilodrostat was continued, typically with decreasing doses.

Potential risks of osilodrostat treatment in study population

Potential risks of treatment with osilodrostat in patients with Cushing's disease include: QT prolongation, adrenal insufficiency, AEs related to the accumulation of precursor molecules, including: increased or decreased blood pressure, hypokalemia or hyperkalemia, hyponatremia, weight gain, edema, and increase in the synthesis of sex steroids (primarily adrenal androgens in women) that may lead to menstrual changes and hirsutism in women and acne in men and women. Corticotroph tumor progression, with or without compressive symptoms, is another potential risk. Skin rash has also been observed.

Mitigation of the potential risks related to osilodrostat treatment include: frequent study visits with careful monitoring for adverse events and toxicities including those that have been observed in previous studies with osilodrostat; vital signs, blood chemistry including urine, serum, and salivary cortisol levels, plasma ACTH, electrolytes, renal and liver function, fasting lipid profiles, HbA1c, sex steroid levels (testosterone, estradiol, adrenal androgens), aldosterone and immediate precursor levels, safety ECGs at the time of C_{max}, pituitary MRI scans, and bone mineral density.

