10.5.3.4 Other safety data

ECG

ECG data will be summarized with

- shift table baseline to worst on-treatment result for overall assessments
- Number and percentage of patients with clinically notable QT/QTcF interval values will be summarized.
- listing of ECG evaluations for all patients with at least one abnormality.

Vital signs

Vital signs (supine BP, HR & temperature) reporting of results will include

- shift table baseline to worst on-treatment result
- table with descriptive statistics at baseline, one or several post-baseline time points and change from baseline to this/these post-baseline time points.

Tumor volume and longest dimension

Tumor volume and longest dimension will be evaluated as defined in [Section 7.2.2.6](#)

The longest dimension (in mm) will be summarized as absolute values and actual and percent change from baseline in longest dimension. The tumor invasiveness is also evaluated, in terms of the prevalence of tumors with extension outside sella turcica and/or invasion into surrounding structures at baseline and during the study (new onset/disappearance).

In addition, if the tumor volume is evaluated, a descriptive summary of actual tumor volumes as well as actual and percent change from baseline in tumor volumes will be provided.

Columbia Suicide Severity Reporting Scale (C-SSRS)

C-SSRS data will be mapped to Columbia Classification Algorithm for Suicide Assessment (C-CASA) as per FDA guidance on suicidality ([Food and Drug Administration 2010](#)). The proportion of patients who have completed suicide, suicide attempt, preparatory actions toward imminent suicidal behavior, suicidal ideation, and self-injurious behavior without suicidal intent will be summarized by treatment arm. The number of patients with SAEs referring to a positive suicidal evaluation will be summarized by treatment arm.

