2.8.4.3 Tumor volume and longest dimension

For tumor volume evaluated by MRI (or CT) by central assessment of an independent neuroradiologist, descriptive summary of actual tumor volumes as well as its change from baseline will be provided at visits where evaluation is scheduled (Week 26, 48, 72, and 96). The independent neuroradiologist measured the tumor volume, when it cannot be easily distinguished, the whole pituitary gland was measured. For the analysis, only measurements of the tumor volume are used.

Patients with pituitary volume assessments at baseline will be monitored and measured at the pre-specified timepoints. Patients with no visible or measurable pituitary tumour at baseline will be assessed at all timepoints whether a tumour becomes visible and it can be measured accordingly. Patients will be assessed whether the pituitary tumour is within or goes beyond the sella turcica at each time points of MRI assessment. Measurements and available information about new lesions of patients with only pituitary gland dimensions at baseline will be listed.

[figure not shown]

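### The core SAP omits or narrows tumour analyses that the protocol specifies (extension/invasion, percent change, longest dimension), the final SAP restores them only in part, and neither declares the departure

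*SAP*

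**What the plan says.** **Protocol 10.5.3.4 (Other safety data)** plans three outputs.

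- Longest dimension, without condition: "The longest dimension (in mm) will be summarized as absolute values and actual and percent change from baseline in longest dimension".
- Invasiveness: "The tumor invasiveness is also evaluated, in terms of the prevalence of tumors with extension outside sella turcica and/or invasion into surrounding structures". This applies to the baseline scan and to later scans, with new onset and disappearance.
- If volume is evaluated, a descriptive summary in which "actual and percent change from baseline in tumor volumes will be provided".

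**Core SAP 2.8.4.3** plans a "descriptive summary of actual tumor volumes as well as its change from baseline will be provided at visits where evaluation is scheduled", at Weeks 26, 48, 72 and 96 and for the overall study period only. Longest dimension is the fallback: "For MRI (or CT) images that are not interpretable for tumor volume, the longest dimension (in mm) will be summarized instead". The section says nothing about extension outside the sella or invasion, and does not mention percent change.

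**Final SAP 2.8.4.3** keeps the same volume summary. It explains that the whole gland was measured where the tumour could not be distinguished, and adds "For the analysis, only measurements of the tumor volume are used". It assesses at each MRI whether the tumour lies within or beyond the sella, checks for newly visible tumours, and lists data for patients who had only gland dimensions at baseline. Its heading still names longest dimension, but no dimension summary follows.

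**Section 4 of each SAP** (changes to protocol-specified analyses) covers only grouping by arm and period. Neither mentions tumour analyses.

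**The concern.** Tumour growth is a recognised hazard of this treatment. Protocol 2.6 states: "Corticotroph tumor progression, with or without compressive symptoms, is another potential risk". Protocol 8.1.3 makes pituitary tumour enlargement a group of adverse events of special interest. The protocol's schedule has no on-treatment pituitary MRI in Period 1, so there is no placebo comparison on imaging. Within-patient change is then the main imaging evidence.

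Three things weaken that evidence in the core report.

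- The table of extension and invasion, which the protocol requires, is absent.
- Absolute volume change is the only change measure named, and large tumours dominate its mean.
- The choice between volume and dimension is made image by image, so a patient can have a value at both scans and a change on neither scale.

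The departure is also undeclared, so a reader of the core report could not tell that protocol analyses had been left out.

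**Working it through.** The plan gives no sample size or numerical target for the tumour analysis, so there is no figure to reproduce. The check is a comparison of texts, then an illustration of the consequence with assumed sizes.

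**1. Texts side by side**

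| Output | Protocol 10.5.3.4 | Core SAP 2.8.4.3 | Final SAP 2.8.4.3 |
|---|---|---|---|
| Volume: value and change | Yes, if evaluated | Yes | Yes |
| Volume: percent change | Yes, if evaluated | Not named | Not named |
| Longest dimension: value, change, percent change | Yes, unconditional | Only for images without a usable volume; no change named | No summary planned |
| Extension outside the sella | Yes | None | Assessed at each MRI |
| Invasion into surrounding structures | Yes | None | None |
| New onset / disappearance | Yes | None | Newly visible tumours assessed; no onset/disappearance table |
| Declared in Section 4 | – | No | No |

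**2. Timing.** Protocol Amendment 1 (20-Nov-2017) added both the serum, salivary and hair cortisol objective and the evaluation of extension and invasion. The core SAP amendment of 01-Apr-2019 took up the cortisol objective but not the tumour item, so the order of the documents does not explain the gap.

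**3. Unpaired scans.** Change needs the same measure at both scans. With volume at baseline and only dimension at Week 48, or the reverse, the core rule gives no volume change and no dimension change. The documents do not say how many patients this affects; it could be none.

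**4. Absolute against percent change.** Assume spherical tumours, with volume = π × d³ / 6. Small lesions are plausible, because inclusion criterion 3c provides a route for tumours of 6 mm or less.

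- d = 6 mm: 113.1 mm3
- d = 9 mm: 381.7 mm3
- d = 20 mm: 4188.8 mm3

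Growth from 6 to 9 mm is 381.7 − 113.1 = +268.6 mm3, which is 268.6 / 113.1 = +238% in volume and +50% in diameter. A 20 mm tumour needs only 268.6 / 4188.8 = 6.4% growth to give the same absolute change, so absolute change does not separate the two.

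Now take nine 6 mm tumours each growing 25% in volume and one 20 mm tumour shrinking 10%:

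- change per small tumour: 0.25 × 113.1 = +28.3 mm3
- change in the large tumour: −0.10 × 4188.8 = −418.9 mm3
- mean absolute change: (9 × 28.27 − 418.88) / 10 = −16.4 mm3
- mean percent change: (9 × 25 − 10) / 10 = +21.5%
- median absolute change: +28.3 mm3

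The mean has the wrong sign for nine of the ten tumours; the median does not.

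**5. Does losing dimension hide growth?** Not where both scans have a volume. Isotropic volume growth of 20%, 25%, 50% and 100% corresponds to diameter growth of only 6.3%, 7.7%, 14.5% and 26.0%. A 10 × 8 × 6 mm ellipsoid growing to 10 × 10 × 6 mm gains 25% in volume with no change in longest dimension. In these examples volume responds more than dimension does. The loss from restricting dimension falls on patients who lack a volume at one or both scans.

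**The case against.** The strongest reply is that little would be hidden.

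- Core SAP 2.1 summarises continuous data by mean, SD, median, minimum and maximum. In the ten-tumour example the median of +28.3 mm3 shows the growth.
- Volume responds at least as much as longest dimension where it exists at both scans, and protocol 7.2.2.5 itself accepts central screening by either measure. Putting volume first is defensible.
- Adverse events of special interest are tabulated, all scheduled pituitary imaging is read centrally, and protocol 7.1.4 has a discontinuation criterion for symptomatic or compressive growth confirmed by MRI.
- The core SAP uses the word change loosely. Its Table 1-1 promises percent change for mUFC and the cardiometabolic parameters, while the matching method sections say only change. Silence in 2.8.4.3 is therefore weak evidence that percent change was deliberately removed.
- No hypothesis test depends on these tables.

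All of this stands as a limit on the consequence. It does not supply the missing extension/invasion table, give a change value to patients with unlike measures, or declare the departure. On percent change, core SAP 2.7.7 and 2.7.8 do write percentage change explicitly, so 2.8.4.3 at least leaves it unspecified where the protocol requires it.

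A reader might also infer that the final SAP abandons dimension and invasiveness altogether, or expels patients who have only a tumour dimension. The text does not go that far. The sentence "For the analysis, only measurements of the tumor volume are used" directly follows the remark about measuring the whole gland, so it mainly contrasts tumour with gland. The section describes no group of dimension-only tumours, and beyond-sella status is assessed.

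**Conclusion.** The point holds as an undeclared departure from the protocol's tumour safety analyses.

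- **Core SAP:** it omits the extension/invasion output, does not name percent change, and summarises longest dimension only for images without a usable volume.
- **Final SAP:** it recovers beyond-sella status and newly visible tumours, but not the dimension summary, percent change, invasion into surrounding structures, or a new-onset/disappearance table.

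A reader might conclude that tumour growth would be missed. The documents do not support that, because volume change with median and range, adverse-event reporting and central reading all remain. What they support is that growth would be described less well: the core report lacks a required table, the mean of absolute change is governed by the largest tumours, and some patients may have no change value.

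The textual findings need no assumption. The −16.4 mm3 against +21.5% contrast rests on assumed spherical tumours and assumed sizes, and shows only what can happen. The number of patients with unlike measures cannot be derived from the documents and could be zero. The primary and key secondary analyses are unaffected. The gap still merits correction, because it concerns a named risk.

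**What to change.** **Core SAP 2.8.4.3**

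- Add a baseline-by-visit table of extension outside the sella and/or invasion, with new onset and disappearance.
- Add percent change beside absolute change in volume.
- Summarise longest dimension (value, change, percent change) for every measurable tumour at each scheduled scan.
- Calculate change only between like measures in the same patient, and report how many patients have no like pair.

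**Final SAP 2.8.4.3**

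- Add percent change, the longest-dimension summary, and the invasion and new-onset/disappearance table to the beyond-sella assessment already there.

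**Section 4 of each SAP**

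- List any departure that is kept, with its reason.

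No instruction on whole-gland volumes is needed in the core SAP, which already specifies tumour volume. The cost is SAP wording and a few descriptive tables. The scans are already reviewed centrally and the protocol already calls for these outputs, so no new patient assessments are needed.
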